6.12. End of Study

The end of the study will be the last participant's last observation (or visit).

6.13. Poststudy Care

The long-term care of the participant will remain the responsibility of their primary treating physician. Remdesivir is being supplied with curative intent. There is no provision for poststudy availability.

CCI

[REDACTED]

[REDACTED]

[REDACTED]

7. ADVERSE EVENTS AND TOXICITY MANAGEMENT

7.1. Definitions of Adverse Events and Serious Adverse Events

7.1.1. Adverse Events

An AE is any untoward medical occurrence in a clinical study participant administered an investigational drug, which does not necessarily have a causal relationship with the treatment. An AE can therefore be any unfavorable and/or unintended sign, symptom, or disease temporally associated with the use of an investigational drug, whether or not the AE is considered related to the investigational drug. Adverse events may also include pretreatment or posttreatment complications that occur as a result of protocol-specified procedures or special situations (Section 7.1.3).

An AE does not include the following:

- Medical or surgical procedures such as surgery, endoscopy, tooth extraction, and transfusion. The condition that led to the procedure may be an AE and must be reported
- Preexisting diseases, conditions, or laboratory abnormalities present or detected before the screening visit that do not worsen
- Situations where an untoward medical occurrence has not occurred (eg, hospitalization for elective surgery, social and/or convenience admissions)
- Overdose without clinical sequelae (Section 7.1.3)
- Any medical condition or clinically significant laboratory abnormality with an onset date before the informed consent form (ICF) is signed and not related to a protocol-associated procedure is not an AE but rather considered to be preexisting and should be documented as medical history.

Preexisting events that increase in severity or change in nature after investigational drug initiation or during or as a consequence of participation in the clinical study will also be considered AEs.

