4.2. Inclusion Criteria

Participants must meet all of the following inclusion criteria to be eligible for participation in this study:

- 1) SARS-CoV-2 positive as determined by polymerase chain reaction (PCR) or other commercially available or public health assay (eg, nucleic acid amplification test and antigen tests) in any respiratory specimen
- 2) Hospitalized for COVID-19
- 3) Age \geq 12 years and weighing at least 40 kg
- 4) O₂ saturation \leq 94% on room air or requiring O₂ supplementation OR radiographic evidence of pulmonary infiltrates for COVID-19
- 5) Have either:
 - a) Severely reduced kidney function (eGFR $<$ 30 mL/min/1.73 m²), using the Chronic Kidney Disease Epidemiology Collaboration (CKD-EPI) and revised Schwartz equations for adults and adolescents, respectively, including people with ESKD requiring chronic dialysis but not people requiring RRT for AKI {[Levey 2009](#), [Schwartz 2009](#)}

Adults: $eGFR \text{ (mL/min/1.73 m}^2\text{)} = 141 \times \min(\text{SCr}/\kappa, 1)^\alpha \times \max(\text{SCr}/\kappa, 1)^{-1.209} \times 0.993^{\text{Age}} \times 1.018 \text{ [if female]} \times 1.159 \text{ [if African American]}$

$\kappa = 0.7$ for females; 0.9 for males

$\alpha = -0.329$ for females; -0.411 for males

Adolescents (age 12–17 years): $eGFR \text{ (mL/min/1.73 m}^2\text{)} = (0.41 \times \text{Height in cm}) / \text{SCr}$

SCr in mg/dL, age in years

(See [Appendix 7](#) for web links to adult and adolescent eGFR calculators), OR

- b) Ongoing AKI: defined as a 50% increase in SCr within a 48-hour period that is sustained (ie, requires confirmatory SCr) for ≥ 6 hours despite supportive care
- 6) Willing and able to provide written informed consent, or with a legal representative who can provide informed consent, or enrolled under International Council for Harmonisation (of Technical Requirements for Pharmaceuticals for Human Use) (ICH) E6(R2) 4.8.15 emergency use provisions as deemed necessary by the investigator (age ≥ 18) prior to performing study procedures
- 7) The interval between COVID-19 symptoms onset and randomization is no more than 10 days
- 8) Male participants and female participants of childbearing potential who engage in heterosexual intercourse must agree to use protocol-specified method(s) of contraception as described in [Appendix 4](#)

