7.3.2. Adverse Events

Following initiation of study medication, collect all AEs, regardless of cause or relationship, throughout the duration of the study, including the protocol-required posttreatment follow-up period. This must be reported on the eCRFs as instructed.

All AEs and clinically significant laboratory abnormalities should be followed until resolution or until the AE is stable, if possible. Gilead may request that certain AEs be followed beyond the protocol-defined follow-up period.

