7.3.3. Serious Adverse Events

All SAEs, regardless of cause or relationship, that occur after the participant first consents to participate in the study (ie, signing the ICF) and throughout the duration of the study, including the posttreatment follow-up visit, must be reported on the applicable eCRFs and Gilead GLPS (formerly known as Pharmacovigilance and Epidemiology) as instructed below in this section. This also includes any SAEs resulting from protocol-associated procedures performed after the ICF is signed.

Any SAEs and deaths that occur after the posttreatment follow-up visit but within 30 days of the last dose of investigational drug, regardless of causality, should also be reported.

Investigators are not obligated to actively seek SAEs after the protocol-defined follow-up period; however, if the investigator learns of any SAEs that occur after the protocol-defined follow-up period has concluded and the event is deemed relevant to the use of investigational drug, the investigator should promptly document and report the event to Gilead GLPS.

Instructions for reporting SAEs are described in Section [7.4.1](#).

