7.4.1.1. Electronic Serious Adverse Event Reporting Process

- Electronic Serious Adverse Event Reporting Process Site personnel will record all SAE data on the applicable eCRFs and from there transmit the SAE information to Gilead GLPS within 24 hours of the investigator’s knowledge of the event from ICF signature throughout the duration of the study, including the protocol-required posttreatment follow-up period.

- If it is not possible to record and transmit the SAE information electronically, record the SAE on the paper SAE reporting form and transmit within 24 hours:

Gilead GLPS

Email: PPD

or

Fax: PPD

- If an SAE has been reported via a paper form because the eCRF database has been locked, no further action is necessary. If the database is not locked, any SAE reported via paper must be transcribed as soon as possible on the applicable eCRFs and transmitted to Gilead GLPS.

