9.1.4. Informed Consent

The investigator is responsible for obtaining written informed consent from each individual participating in this study after adequate explanation of the aims, methods, objectives, and potential hazards of the study before undertaking any study-related procedures. The investigator must use the most current IRB- or IEC-approved ICF for documenting written informed consent. Each ICF (or assent as applicable) will be appropriately signed and dated by the participant or the participant's legally authorized representative, the person conducting the consent discussion, and an impartial witness (if required by IRB or IEC or local requirements).

The ICF will inform participants about genomic testing and/or planned sample retention. ^{CCI}

CCI

The results of the tests done on the samples will not be given to the participant or the investigator.

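### For adults enrolled under the emergency provision, SAE reporting and the medical-history exclusion start at ICF signature, while post-dose AE collection starts at first drug

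*Protocol*

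**What the plan says.** **Enrolment.** Criterion 6 (protocol 4.2, repeated in the synopsis) gives three alternatives: the participant consents, a legal representative consents, or, for adults only, enrolment proceeds under the ICH E6(R2) "4.8.15 emergency use provisions as deemed necessary by the investigator". Section 6.2.1 lists written consent or assent as a screening step. Section 9.1.4 makes the investigator responsible for "obtaining written informed consent from each individual participating in this study" before any study-related procedure. Neither section mentions the emergency route.

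**Rules tied to consent or ICF signature.**
- 7.1.1, last exclusion bullet: a condition "with an onset date before the informed consent form (ICF) is signed and not related to a protocol-associated procedure is not an AE"; it counts as preexisting and is documented as medical history.
- 7.3.1: pre-dose collection begins after informed consent.
- 7.3.3: the SAEs to be reported are those "that occur after the participant first consents to participate in the study (ie, signing the ICF".
- 7.4.1.1: the 24-hour transmission limit runs from the investigator's "knowledge of the event from ICF signature throughout the duration of the study".

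**Rules tied to study drug.**
- 7.3.2: "Following initiation of study medication, collect all AEs, regardless of cause or relationship".
- 7.3.4: special situation reports run from drug initiation.
- Protocol 8.6 and 8.6.2 and SAP 7.1.5.1: safety summaries and treatment-emergent AEs run from first dose or drug start.

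**The concern.** The consent-anchored rules work only if consent always precedes dosing, and criterion 6 allows a route on which it may not. On that route the interval between first dose and signature has two incompatible starting points for safety data, and no section says which governs.

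At stake are the prompt reporting of serious events to the sponsor's safety group and the completeness of the AE record for the same interval. Dosing lasts at most 5 days, so a short gap can cover much or all of it. Protocol 7.7 notes that reactions occur during and after infusion. Clinical events of that kind have no laboratory trace to fall back on. The study is motivated by accumulation of a renally cleared excipient (protocol 1.3), so events close to dosing are of direct interest.

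**Working it through.** No formula applies, and the plan gives no figure to reproduce. The check sets every consent, AE and SAE start point in the two documents side by side and applies them to an event that occurs after first dose and before any ICF is signed. That such an interval exists is an inference from criterion 6; the documents do not describe a later signing step.

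1. **New non-serious event.** Section 7.3.2 requires collection. The 7.1.1 bullet says it is not an AE. This is a direct contradiction. The bullet's exception for protocol procedures does not clearly resolve it, because 7.2.1 assesses drug causality separately from procedure causality and gives venipuncture as its procedure example.

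2. **Worsening of a condition present before dosing.** The closing sentence of 7.1.1 makes it an AE, because it worsened after drug initiation. Section 7.3.2 agrees, so there is no gap here.

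3. **Serious event.** Sections 7.3.3 and 7.4.1.1 both start at signature, so neither triggers the 24-hour report. Section 7.3.2 would still place the event on the AE form, but it governs collection and not expedited transmission. If no ICF is ever signed, for example because of an early death, the 7.3.3 start point is never reached.

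4. **Treatment-emergent tables.** The windows in protocol 8.6.2 and SAP 7.1.5.1 open at first dose or drug start. An event recorded as an AE is counted whether or not an ICF had been signed. It drops out only if a site applied 7.1.1 and filed it as medical history.

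5. **SAE reconciliation.** SAP 7.1.4 compares SAEs in the clinical database with the safety database. That can reveal an SAE entered on the form but not transmitted, although later than the 24-hour limit. An event filed as medical history and never transmitted is in neither source, so the comparison cannot find it.

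6. **Data that do not depend on AE entry.** Deaths count in the primary endpoint from first dose (protocol 8.5.1) and in the treatment-emergent death summary (SAP 7.1.6). Graded laboratory abnormalities (SAP 7.2.2.1) and liver-test thresholds (SAP 7.2.3) come from laboratory values. Renal replacement therapy is listed separately (SAP 7.5).

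The size can only be bounded. If nobody entered by this route, or all signed before dosing, no event is affected. At the other extreme, every SAE between first dose and signature in these participants falls outside 7.3.3 as written, and every new AE in that interval is open to misfiling.

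**The case against.** The best defence is that the 7.1.1 bullet should be read in context. The governing definition in the same section covers any event "temporally associated with the use of an investigational drug, whether or not the AE is considered related to the investigational drug", and the bullet concerns conditions regarded as preexisting. Section 6.2.1 sends to medical history other untoward occurrences seen during screening, which comes before randomization. Section 7.3.2 is explicit and starts at study medication. A sensible site would record a new post-dose reaction as an AE. This has force: misfiling is a possible result of contradictory text, not something the protocol uniformly requires. It does not remove the contradiction, and it leaves the SAE start point untouched.

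The defence can add that criterion 6 speaks of study procedures coming afterwards, that a legally authorized representative may sign under 9.1.4, and that no deferred-signature step appears in the material available. Dosing before signature is therefore inferred. That stands as a limit on the size. But the emergency route is worded as an alternative to both forms of consent, so the safety rules need a start point for it.

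A reader might go further and infer any of the following, which the documents do not support:
- **That all AE rules start at signature, so post-dose events before consent are never reported.** Post-dose AE collection, special situation reports and the treatment-emergent definitions start at drug.
- **That early renal or hepatic toxicity is undercounted.** Laboratory tables do not need an AE entry, and the blinded DMC listings carried Grade 3 or higher AEs as well as SAEs (SAP 2.2).
- **That these participants are the sickest in the trial.** Nothing says so, and exclusion criterion 3 removes those on invasive or noninvasive ventilation or ECMO.

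**Conclusion.** The contradiction holds and is more than missing detail. For adults on the criterion 6 emergency route, following 7.3.3 and 7.4.1.1 as written leaves an SAE after first dose but before signature with no expedited report. A new AE in the same interval is collectable under 7.3.2 and excluded under 7.1.1. Section 9.1.4 conflicts with criterion 6 on whether such enrolment is possible at all.

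The contradiction is certain from the text; its effect is not. Loss from the treatment-emergent tables requires three things: emergency enrolment, dosing before signature, and a site that filed the event as medical history. Neither the number of such enrolments nor any delay to signature is stated, so the effect may be nil. No estimate of undercounting can be justified. The point merits correction because the remedy is cheap, but it is not evidence that safety data were lost.

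**What to change.** **Protocol wording.** In 7.1.1, 7.3.1, 7.3.3 and 7.4.1.1, start AE and SAE collection and reporting at the earliest of consent, first study procedure or first dose. State in 7.1.1 that no new event with onset on or after first dose is medical history. Add the criterion 6 route to 6.2.1 and 9.1.4, so that the consent sections and the eligibility criteria agree. The protocol already uses drug initiation as a start point in 7.3.2 and 7.3.4, so this introduces no new concept.

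**Data review.** SAP 2.4 records that enrolment has stopped, so new wording cannot protect further participants and the data checks are what can still take effect. Before data finalization:
- identify participants enrolled under the emergency provision;
- run an edit check for medical history entries with onset on or after first dose, query each one (using onset time for entries on the first-dose date), and move confirmed new events to the AE dataset before the treatment-emergent tables are run;
- confirm that every SAE in these participants reached the safety database, going back to source records and not relying only on the SAP 7.1.4 comparison.

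**Cost.** Protocol text, a form-completion note and one programmed check, with no extra visits. The downside is a few more queries and expedited reports.

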7.1.2. Serious Adverse Events

An SAE is defined as an event that, at any dose, results in the following:

- Death
- A life-threatening situation (Note: The term “life-threatening” in the definition of “serious” refers to an event in which the participant was at risk of death at the time of the event; it does not refer to an event that hypothetically might have caused death if it were more severe.)

- Inpatient hospitalization or prolongation of existing hospitalization
- Persistent or significant disability/incapacity
- A congenital anomaly/birth defect
- A medically important event or reaction: Such events may not be immediately life-threatening or result in death or hospitalization but may jeopardize the participant or may require intervention to prevent one of the other outcomes constituting SAEs. Medical and scientific judgment must be exercised to determine whether such an event is a reportable under expedited reporting rules. Examples of medically important events include intensive treatment in an emergency room or at home for allergic bronchospasm; blood dyscrasias or convulsions that do not result in hospitalization; and development of drug dependency or drug abuse.

7.1.3. Investigational Drugs and Gilead Concomitant Therapy Special Situations Reports

Special situation reports (SSRs) include all reports of medication error, abuse, misuse, overdose, occupational exposure, drug interactions, exposure via breastfeeding, unexpected benefit, transmission of infectious agents via the product, counterfeit or falsified medicine, and pregnancy regardless of an associated AE.

Medication error is any unintentional error in the prescribing, dispensing, preparation for administration or administration of an investigational drug while the medication is in the control of a health care professional, patient, or consumer. Medication errors may be classified as a medication error without an AE, which includes situations of missed dose, medication error with an AE, intercepted medication error, or potential medication error.

Abuse is defined as persistent or sporadic intentional excessive use of an investigational drug by a participant.

Misuse is defined as any intentional and inappropriate use of an investigational drug that is not in accordance with the protocol instructions or the local prescribing information.

An overdose is defined as an accidental or intentional administration of a quantity of an investigational drug given per administration or cumulatively which is above the maximum recommended dose as per protocol or in the product labeling (as it applies to the daily dose of the participant in question). In cases of a discrepancy in drug accountability, overdose will be established only when it is clear that the participant has taken the excess dose(s). Overdose cannot be established when the participant cannot account for the discrepancy, except in cases in which the investigator has reason to suspect that the participant has taken the additional dose(s).

Occupational exposure is defined as exposure to an investigational drug as a result of one's professional or nonprofessional occupation.

Drug interaction is defined as any drug/drug, drug/food, or drug/device interaction.

Unexpected benefit is defined as an unintended therapeutic effect where the results are judged to be desirable and beneficial.

Transmission of infectious agents is defined as any suspected transmission of an infected agent through a Gilead investigational drug.

Counterfeit or falsified medicine: Any investigational drug with a false representation of (a) its identity, (b) its source, or (c) its history.

7.2. Assessment of Adverse Events and Serious Adverse Events

The investigator or qualified subinvestigator is responsible for assessing AEs and SAEs for causality and severity, and for final review and confirmation of accuracy of event information and assessments.

7.2.1. Assessment of Causality for Investigational Drugs and Procedures

The investigator or qualified subinvestigator is responsible for assessing the relationship to investigational drug using clinical judgment and the following considerations:

- **No:** Evidence exists that the AE has an etiology other than the investigational drug. For SAEs, an alternative causality must be provided (eg, preexisting condition, underlying disease, intercurrent illness, concomitant medication).
- **Yes:** There is reasonable possibility that the AE may have been caused by the investigational drug.

It should be emphasized that ineffective treatment should not be considered as causally related in the context of AE reporting.

The relationship to study procedures (eg, invasive procedures such as venipuncture or biopsy) should be assessed using the following considerations:

- **No:** Evidence exists that the AE has an etiology other than the study procedure.
- **Yes:** The AE occurred as a result of protocol procedures (eg, venipuncture).

7.2.2. Assessment of Severity

The severity of AEs will be graded using the Division of AIDS (DAIDS) Toxicity Grading Scale, Version 2.1. For each episode, the highest grade attained should be reported as defined in the Toxicity Grading Scale ([Appendix 5](#)).

7.3. Investigator Reporting Requirements and Instructions

7.3.1. Requirements for Collection Prior to Investigational Drug Initiation

After informed consent, but prior to initiation of study medication, the following types of events must be reported on the applicable eCRFs: all SAEs and AEs related to protocol-mandated procedures.

7.3.2. Adverse Events

Following initiation of study medication, collect all AEs, regardless of cause or relationship, throughout the duration of the study, including the protocol-required posttreatment follow-up period. This must be reported on the eCRFs as instructed.

All AEs and clinically significant laboratory abnormalities should be followed until resolution or until the AE is stable, if possible. Gilead may request that certain AEs be followed beyond the protocol-defined follow-up period.

7.3.3. Serious Adverse Events

All SAEs, regardless of cause or relationship, that occur after the participant first consents to participate in the study (ie, signing the ICF) and throughout the duration of the study, including the posttreatment follow-up visit, must be reported on the applicable eCRFs and Gilead GLPS (formerly known as Pharmacovigilance and Epidemiology) as instructed below in this section. This also includes any SAEs resulting from protocol-associated procedures performed after the ICF is signed.

Any SAEs and deaths that occur after the posttreatment follow-up visit but within 30 days of the last dose of investigational drug, regardless of causality, should also be reported.

Investigators are not obligated to actively seek SAEs after the protocol-defined follow-up period; however, if the investigator learns of any SAEs that occur after the protocol-defined follow-up period has concluded and the event is deemed relevant to the use of investigational drug, the investigator should promptly document and report the event to Gilead GLPS.

Instructions for reporting SAEs are described in Section [7.4.1](#).

